## 2. STUDY PROCEDURES

#### a. Procedures

Screening will occur during a regular clinic visit. Each participant will undergo an MRI after a single intravenous injection of ferumoxytol at a dose of 5 mg Fe/kg body weight. Precontrast images will be added when feasible. Postcontrast images will be obtained directly after and/or 1-2 days after ferumoxytol administration. In patients with osteonecrosis who undergo a surgical decompression procedure with implantation of bone marrow derived cells into the osteonecrosis, a ferumoxytol-enhanced MRI will be performed before surgery and follow up MR scans will be obtained at 1-6 months after the surgery. When available, routinely obtained biopsy and/or surgical resection samples of bone lesions will be examined by our collaborating pathologist for presence of mesenchymal stromal cells, macrophages and possibly iron content in samples that happen to be obtained shortly after the ferumoxytol injection.

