## 6. **PARTICIPANT POPULATION**

## a. Planned Enrollment

(i) Target is 20 participants: 10 patients with osteonecrosis receiving ferumoxytol; 10 patients with osteonecrosis not receiving ferumoxytol
(ii) single site study; 20.
(iii) pediatric and young adult patients (8 - 40 years), male or female subjects, referred to the cancer center for assessment of an osteonecrosis lesion in the bone.
iv) control pediatric and young adult patients (8 - 40 years), male or female subjects, with osteonecrosis who receive an MRI without ferumoxytol
Inclusion criteria: Osteonecrosis
Age, Gender, and Ethnic Background:
8 to 40 years of age
any gender
any ethnicity

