#### g. Eligibility Criteria

i. Inclusion Criteria

8-40 years of age, suspected or confirmed diagnosis of osteonecrosis

ii. Exclusion Criteria

contraindication to MRI (metal implants), need for sedation or anesthesia, claustrophobia. Hemosiderosis/ hemochromatosis as defined by decreased T2-signal of liver will

exclude patients from arm 1 (ferumoxytol-MRI). Patients with hemosiderosis/hemochromatosis can still be included in the osteonecrosis study and would undergo MRI evaluation without ferumoyxtol (control group).

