## 10. STATISTICAL PLAN

All experiments were analyzed using R version 3.4.4. The number of patients per experimental group were determined by power analyses. Signal-to-noise ratios (SNR) and T2 relaxation times were pairwise compared between osteonecrosis lesions with and ferumoxytol administration, and between decompression track areas with and without visible iron-labeled cells, using a mixed-effects model including a random effect term accounting for correlation among the measures within a same patient. A Fisher exact test was applied for comparison of clinical outcomes of osteonecrosis with and without ferumoxytol enhancement. In addition, differences in time to progression of osteonecrosis from surgery between bone lesions that did or did not enhance with ferumoxytol were assessed by log-rank tests. Because of the small sample size and exploring purpose of this study, a P < 0.05 without adjustment for multiple comparisons was considered to indicate significant differences between experimental groups.

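### Decompression-track areas are sorted by visible iron and then compared on T2 and SNR, with no stated comparison by ferumoxytol exposure, so a difference cannot show that the signal comes from labeled cells

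*Combined protocol and SAP*

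**What the plan says.** Section 10 (Statistical Plan) states two imaging comparisons. "Signal-to-noise ratios (SNR) and T2 relaxation times were pairwise compared" first for lesions, "pairwise compared between osteonecrosis lesions with and ferumoxytol administration" (the word for the unexposed group seems to have dropped out), and second "between decompression track areas with and without visible iron-labeled cells". Both use "a mixed-effects model including a random effect term accounting for correlation among the measures within a same patient". The first contrast is by exposure. The second is by what is seen on the image. Section 10 gives no criterion for visible iron, no masking of the reader, and no statement of which patients supply the areas without it.

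Section 3.a (Past Experimental and/or Clinical Findings) supplies the reasoning behind the label: marrow cells take up the nanoparticles and become dark on T2-weighted images.

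Section 6.a (Planned Enrollment) provides "10 patients with osteonecrosis receiving ferumoxytol; 10 patients with osteonecrosis not receiving ferumoxytol". It defines controls as osteonecrosis patients who have MRI without the agent and does not mention surgery. Section 2.a (Procedures) says that for decompression patients "follow up MR scans will be obtained at 1-6 months after the surgery", after a ferumoxytol-enhanced MRI before surgery. It does not mention operated controls.

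Section 6.g (Eligibility Criteria) excludes from the ferumoxytol arm patients with "Hemosiderosis/ hemochromatosis as defined by decreased T2-signal of liver" and allows them into the control group.

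**The concern.** Calling an area iron-labeled states where the signal comes from. The planned comparison does not test that source. If darkness on the image decides the group, and T2 and SNR are then measured on the same areas, the groups will tend to differ whether the low signal comes from ferumoxytol-labeled cells or from something else.

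The protocol itself accepts, for the liver, that iron unrelated to ferumoxytol lowers T2 signal (section 6.g). Tissue will not reliably settle the source. Under section 2.a, pathology uses routine samples when they happen to be available, and iron content is only a possible assessment in samples taken shortly after injection.

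What is at stake is the attribution of track signal to labeled cells. The secondary endpoint (section 2.g) seeks ferumoxytol-MRI features of response to decompression and cell transplant. A track feature put forward for that purpose would need to be shown to depend on the agent.

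**Working it through.** The plan gives no figure to reproduce on this point. Section 10 says group sizes came from power analyses but reports no effect size, SD or power.

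**1. The two contrasts side by side**

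| | Lesions | Tracks |
|---|---|---|
| Groups formed by | ferumoxytol exposure | visible iron-labeled cells |
| Outcomes | SNR, T2 | SNR, T2 |
| Grouping independent of the outcome? | yes, exposure is set outside the image | no, both come from the image signal |
| Unexposed reference stated? | yes, apparently | no |

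**2. How far the visible split builds in a difference**

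Simulation with no labeled cells in any track: 10 tracks, one per patient, with T2 drawn from a standard normal distribution. The visual read is ρ × T2 + √(1 − ρ²) × noise. The 5 darkest reads form one group and the other 5 the second, compared by a t-test at two-sided 0.05. The by-arm comparison sets the same 10 tracks against 10 control tracks from the same distribution. There were 4,000 runs per setting. The values of ρ, the 5/5 split and one track per patient are assumptions.

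| ρ (read v measured T2) | Visible split, P < 0.05 | By arm, P < 0.05 |
|---|---|---|
| 0 | 4% | 4% |
| 0.3 | 10% | 5% |
| 0.5 | 19% | 5% |
| 0.7 | 39% | 6% |
| 0.9 | 77% | 5% |

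The more closely the eye tracks T2, the more often the planned comparison is significant with no labeled cells present. The by-arm comparison keeps its nominal level, provided the arms do not differ in other sources of iron.

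**3. What control tracks could show**

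Assume one readable track per operated control. With x dark tracks among n, the exact (Clopper-Pearson) 95% upper limit for x = 0 is 1 − 0.025^(1/n).

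- 0 of 10: 1 − 0.025^(1/10) = 30.8%
- 1 of 10: interval 0.3% to 44.5%
- 2 of 10: interval 2.5% to 55.6%
- 0 of 5: 1 − 0.025^(1/5) = 52.2%

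For a two-sided Fisher P below 0.05 at 10 v 10, the ferumoxytol arm needs at least 5 dark tracks if controls have 0, 7 if controls have 1, and 8 if controls have 2. Check of the first: 2 × C(10,5) × C(10,0) / C(20,5) = 2 × 252 / 15,504 = 0.033.

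Illustrative counts, not from the documents: 7/10 v 1/10 gives P = 0.020, v 2/10 gives 0.070, and v 4/10 gives 0.370.

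**4. Continuous outcomes by arm**

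With 10 tracks per arm, a two-sided t-test has 80% power for a difference of about 1.32 SD. Only a large difference in track T2 or SNR would be detected reliably.

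**The case against.** The strongest reply has five parts.

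- **Control tracks may be in the analysis.** Section 10 does not say who supplies the areas without visible iron, so control tracks could be among them. This stands: a reader might infer that control tracks are never used, but the text supports only that no use as a negative control is stated. Pooling them into that group would still give no rate of dark control tracks.
- **There may be no operated controls.** This stands. Neither section 6.a nor section 2.a says that controls have surgery, so the main remedy is conditional.
- **Surgical blood is not in the documents.** This stands. A reader might infer that bleeding will be reported as transplanted cells. Section 6.g concerns iron overload seen in the liver and says nothing about blood in a drilled track at 1-6 months. Residual blood is an assumption, both its presence and its amount. The gap exists for any other cause of low T2.
- **Track iron is not tied to outcome.** This stands. The Fisher and log-rank tests in section 10 use lesion enhancement. The inference that the study's response feature is a surgical artefact is not supported.
- **The control arm is not a clean reference.** This stands. Section 6.g directs patients with iron overload to it, which could raise the control dark rate and lead to over-correction.

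The study is also openly exploratory, and a measured difference between areas that look different is a fair check that the visual read reflects signal. Neither point supplies evidence about where the iron came from.

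**Conclusion.** The concern holds in a limited form. As written, the track comparison groups areas by visible iron and tests them on T2 and SNR, with no stated comparison by ferumoxytol exposure. A significant result cannot by itself be attributed to ferumoxytol-labeled cells. Under the simulation's assumptions, the false-signal rate runs from 4% when the read is unrelated to T2 to 77% when the correlation is 0.9. The true correlation is not given in the documents.

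The reading that visible iron means dark T2 signal rests on section 3.a, because section 10 gives no rule. The Fisher P values at 7/10 v 1, 2 or 4 of 10 use invented counts. They show how much the control rate matters and do not predict a result. Nor do they show that the plan would reach one conclusion in every case, since section 10 states no attribution rule.

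This should be corrected before track signal is interpreted. It does not affect the lesion comparison.

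**What to change.** In section 10:

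1. Define visible iron by an explicit reading rule.
2. Where controls have decompression surgery and follow-up MRI, read their tracks by that rule, mixed with the ferumoxytol scans and masked to arm. State how many such controls there are.
3. Compare the share of tracks with visible iron, and track T2 and SNR, by ferumoxytol exposure. Use the planned mixed model for T2 and SNR, with months since surgery as a covariate.
4. Exclude controls with hemosiderosis or hemochromatosis from this comparison, or flag and show them separately.
5. Report the control dark rate with its exact confidence interval, and attribute track signal to labeled cells only so far as it exceeds that rate.
6. If no or very few controls are operated, describe the areas as T2-dark and make no attribution to labeled cells.

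The cost is reading and analysis time if operated controls and their follow-up scans exist. Section 6 (Planned Duration of the Study) describes follow-up MRI after surgery without limiting it to one arm, and section 7.a lists a follow-up MRI without contrast, but neither confirms control scans. Step 6 needs no control data. The downside is that the attribution claim may become less favourable, and its precision stays limited by the small number of operated controls.

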## I. Planned Duration of the Study

The revised anticipated study duration is until 2026. (i) screening should take 15-30 minutes; (ii) active participation involves two MRI scans for a total of approximately 2-3 hours; (iii) follow up MRI(s) within 1-6 months after decompression surgery will be evaluated to determine clinical outcomes (iv) data analysis will continue until publication in approximately 12 months from initiation.

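### The decompression-track comparison has no term for time since surgery, so time can confound the iron effect if iron visibility and track signal both change between 1 and 6 months

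*Combined protocol and SAP*

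**What the plan says.** Section 10 (Statistical Plan) states that "Signal-to-noise ratios (SNR) and T2 relaxation times were pairwise compared" for two contrasts. The second is "between decompression track areas with and without visible iron-labeled cells". The method is described as "using a mixed-effects model including a random effect term accounting for correlation among the measures within a same patient". No fixed effect for visit or time since surgery is named. Nor does the section say which scans enter, how repeat scans are handled, or what forms a pair.

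On timing, Section 2.a (Procedures) says "follow up MR scans will be obtained at 1-6 months after the surgery". Section 6 (Planned Duration of the Study) says "follow up MRI(s) within 1-6 months after decompression surgery will be evaluated to determine clinical outcomes". Both wordings allow more than one scan per patient, and neither fixes a visit for analysis. In Section 10, time from surgery appears only in the log-rank analysis of "differences in time to progression of osteonecrosis from surgery".

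The planned size (Section 6.a) is: "Target is 20 participants: 10 patients with osteonecrosis receiving ferumoxytol; 10 patients with osteonecrosis not receiving ferumoxytol".

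**The concern.** A decompression track can be imaged only after surgery, so the track data must come from the 1-6 month window, which is six-fold wide. The grouping variable is whether iron is visible, and this may itself depend on when the scan was taken. Section 7.a lists the follow-up MRI as without contrast; if that covers the post-surgery scans, iron seen there is retained label. The track may also change in T2 and SNR as it heals.

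If both happen, areas with iron come mainly from early scans and areas without iron mainly from late ones. The contrast then carries part of the time trend. A patient random intercept absorbs stable differences between patients. It does not absorb the difference between an early and a late scan of one patient.

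The result could be an apparent iron effect where there is none, or a real one hidden by an opposing trend. The comparison bears on the third objective (evaluation of therapy success) and on the secondary endpoint on treatment response.

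**Working it through.** **The plan's own figure.** Section 10 says that group sizes came from power analyses but gives no effect size, SD or power, so 10 per group cannot be reproduced. For scale, a two-sample comparison with 10 per group at two-sided 0.05 and 80% power detects (1.960 + 0.842) × √(2/10) = 1.25 SD (1.32 SD with the t distribution).

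**Inputs from the documents.** Window 1 to 6 months; repeats allowed; patient random effect only; 0.05 level.

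**Assumed inputs (not in the documents).** No true iron effect; scans at 1, 3 and 6 months; two areas per scan; within-patient correlation 0.4; 5 to 10 operated ferumoxytol patients; linear drift of 0.5 or 1 SD over 5 months; iron visibility falling over the window.

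**Step 1: bias.** Bias ≈ slope per month × difference in mean scan time between the two area types. Take visibility of 80% at 1 month and 20% at 6 months. Linear interpolation gives 80 − 60 × 2/5 = 56% at 3 months.

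- Mean scan time, iron visible: (0.80×1 + 0.56×3 + 0.20×6) / 1.56 = 3.68/1.56 = 2.36 months.
- Mean scan time, iron not visible: (0.20×1 + 0.44×3 + 0.80×6) / 1.44 = 6.32/1.44 = 4.39 months.
- Gap: 2.03 months. A 1 SD drift is 0.2 SD per month, so the bias is about 0.2 × 2.03 = 0.41 SD. With a 0.5 SD drift it is about 0.20 SD.

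In the extreme case of every visible area at month 1 and every other at month 6, slopes of 0.1 to 0.3 SD per month give 5 × 0.1 = 0.5 to 5 × 0.3 = 1.5 SD. If mean scan times are equal, the bias is zero.

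**Step 2: false-positive rate.** Simulated mixed models at nominal 5%; ranges span patient numbers and separate runs. With 600 trials, the Monte Carlo standard error is √(0.05×0.95/600) = 0.9 points near 5% and √(0.45×0.55/600) = 2.0 points near 45%.

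| Assumed setting | Patient effect only | With time term |
|---|---|---|
| Three scans, 80% to 20%, 1 SD drift | about 25% (5 patients) to 47% (10 patients); single runs 24-30% and 45-49% | 4-6% |
| Three scans, 80% to 20%, 0.5 SD drift | 11-19% | about 5% |
| Three scans, 70% to 30%, 0.5-1 SD drift | 7-24% | 5-6% |
| Three scans, 60% to 40%, 0.5 SD drift | 6-8% | not run |
| Two scans at random times, 70% to 30%, 0.5 SD drift | 7-8% | not run |
| One scan per patient | 5-8% | not run |
| No trend in visibility | 5% | not run |
| 10 v 10 patients between arms, same timing, 1 SD drift | 5-7% | not run |

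With one scan per patient the rate stays low because the patient intercept is then also a scan intercept. A scan-level random effect is not enough with repeats. With 8 patients in the first setting, rejection was 34.0% with the patient effect only, 28.3% with a scan effect added, and 5.7% with a time term instead.

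**Step 3: unequal timing between two groups of patients.** With 10 patients per group, two areas each, within-patient correlation 0.5 and a slope of 0.2 SD per month, type I error was 0.05, 0.08, 0.16 and 0.30 for mean timing gaps of 0, 1, 2 and 3 months. With a time term it was 0.042 to 0.054 over all slopes and gaps tried.

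**Step 4: power.** With a true 1 SD iron effect opposed by the drift, power with 5-10 patients was about 33-62% without the time term and 75-97% with it.

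**Step 5: same-scan pairs.** When both area types come from the same scan, time cancels. A paired analysis held its level (0.047 to 0.060). The planned model, which leaves drift in the residual, rejected in only about 2-3%; the time term narrowed the standard error by about 14%.

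**The case against.** A reader might infer that the plan pools scans across the window and that healing and fading iron are therefore mixed into its estimate. The documents do not support this. Section 10 does not say which scans enter. No section gives a rate of iron loss or of track change, and Section 3.a calls the contrast effect long lasting.

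Two readings would remove most of the problem. Pairwise may mean areas on the same scan, where time cancels. Alternatively, areas without visible iron may come from the control arm, and nothing suggests that the arms are scanned at different times. Both readings are possible and neither is established: Section 10 applies the same word to lesions with and without ferumoxytol, which Section 6.a places in separate groups of patients.

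The largest rates also need three scans per patient, a schedule that appears nowhere in the documents, together with a marked visibility trend and drift; milder settings give 6-8%. This stands. So does the point that a zero iron effect is an artificial null, since areas are classed by visible iron and iron darkens T2-weighted signal. The bias in the estimate and the loss of power do not depend on that null. Finally, the time term does well partly because the simulated drift is linear, as the term is.

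The stated exploratory purpose is given as the reason for not adjusting for multiple comparisons. It does not address confounding.

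**Conclusion.** The point holds as a conditional risk of confounding, not as demonstrated bias. The stated model has nothing that removes differences in time since surgery, and the scan window and repeats leave room for them. Bias requires that iron visibility and track T2 or SNR both change over 1-6 months, and that the areas compared differ in scan time. Under the assumed values the consequence runs from none or negligible (same-scan pairs, one scan per patient, equal timing between arms) to a bias of about 0.4 SD and a type I error of about 25-47% in the strongest pooled setting. The documents do not show where in that range the trial lies. The change is worth making because it is specific and cheap, and it protects the estimate under either reading of pairwise.

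**What to change.** In Section 10, add time since surgery at the scan (months, continuous) as a fixed effect in the SNR and T2 models for track areas. As a supportive analysis, report the difference between areas with and without visible iron within the same scan, wherever a scan shows both. State the pairing unit in the same sentence.

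The statistical cost is about one degree of freedom and a slightly wider interval when time and visibility are correlated. A linear term may not fully capture non-linear healing; the same-scan difference does not rely on that form.

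No new scans or patients are needed. The documents do not say that surgery and scan dates are recorded, but the time-to-progression analysis implies that they are. Section 10 is written in the past tense, so the change may mean rerunning the track models as well as editing the text.

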## g. Study Endpoint(s)

Endpoint of these examinations is to define distinctive MR signal characteristics of osteonecrosis lesions. Secondary endpoint is to define specific ferumoxytol-MR imaging features that indicate treatment response to decompression surgery and stem cell transplant.

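### Time to progression is compared between lesions by an ordinary log-rank test with no provision for patients who contribute more than one lesion; if any do, the 0.05 level is not assured

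*Combined protocol and SAP*

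**What the plan says.** Section 10 (Statistical Plan) describes three kinds of analysis.

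- SNR and T2 relaxation times are compared with a mixed-effects model that has a "random effect term accounting for correlation among the measures within a same patient".
- For clinical outcomes, "A Fisher exact test was applied for comparison of clinical outcomes of osteonecrosis with and without ferumoxytol enhancement". Whether the unit is the patient or the lesion is not said.
- Differences in time to progression, counted from surgery, "between bone lesions that did or did not enhance with ferumoxytol were assessed by log-rank tests". No stratification, cluster variance, frailty term or index-lesion rule is mentioned.

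A P below 0.05 "without adjustment for multiple comparisons was considered to indicate significant differences between experimental groups".

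Enrolment is counted in patients: "10 patients with osteonecrosis receiving ferumoxytol; 10 patients with osteonecrosis not receiving ferumoxytol" (section 6a). Eligibility (section 6g) sets no limit on lesions and names no index lesion. Surgery concerns a subset: "In patients with osteonecrosis who undergo a surgical decompression procedure with implantation of bone marrow derived cells into the osteonecrosis" (section 2a). Follow-up MRI falls 1-6 months after surgery (sections 2a and 6l).

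**The concern.** The log-rank variance treats every observation as independent. Two lesions in one patient share host, underlying disease, operation and follow-up, so their progression times may well be correlated. Section 10 allows for correlation within a patient in the SNR and T2 model but not in the progression analysis.

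The progression comparison bears on Objective 3 (section 1b) and on section 2g: "Secondary endpoint is to define specific ferumoxytol-MR imaging features that indicate treatment response to decompression surgery and stem cell transplant". If several lesions per patient enter as if independent, a result can be called significant too easily or too rarely. The direction depends on whether enhancement is shared within a patient or differs within a patient, and the documents do not say which applies.

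**Working it through.** **Inputs from the documents.** 20 patients, 10 with and 10 without ferumoxytol (section 6a); significance at 0.05 (section 10; two-sided assumed); last follow-up at 6 months (sections 2a, 6l). Section 10 says group sizes came from power analyses but gives no power, effect, event rate or lesion count, so there is no planned figure to reproduce.

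**Assumed inputs.** 10 patients split 5/5 by enhancement; two lesions each; progression by 6 months 30% or 60%; exponential times censored at 6 months; gamma frailty with variance 2τ/(1 − τ), Kendall τ = 0.2, 0.33 or 0.5.

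**Step 1. Closed form, shared enhancement.** Design effect DE = 1 + (m − 1)ρ, with m lesions per patient and correlation ρ. True size = 2[1 − Φ(1.96/√DE)]. For m = 2:

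- ρ = 0.3: DE = 1.3, size 0.086
- ρ = 0.5: DE = 1.5, size 0.110
- ρ = 0.8: DE = 1.8, size 0.144
- m = 1 or ρ = 0: DE = 1, size 0.050

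**Step 2. Simulated null error of the lesion-level log-rank at 0.05** (20,000 replicates per setting, Monte Carlo standard error at most 0.3 points; a separate run of 6,000 replicates agreed within simulation error).

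| Setting | 60% progression | 30% progression |
|---|---|---|
| One lesion each | 6.0% | 6.2% |
| Two lesions, enhancement shared (τ 0.2, 0.33, 0.5) | 8.6, 11.0, 14.0% | 6.4, 7.5, 9.9% |
| One enhancing and one non-enhancing lesion each | 2.9, 1.6, 0.4% | 3.5, 2.6, 1.3% |
| Enhancement unrelated to patient | 5.5-5.6% | 4.3-4.7% |

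Against the one-lesion baseline, shared enhancement adds 2.6 to 8.0 points at 60% and 0.2 to 3.7 points at 30%.

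**Step 3. More patients.** If operated patients without ferumoxytol count as non-enhancing, more than 10 could enter. With 20 patients split 10/10, two lesions, shared status, a Gaussian copula and 50% progression, the error is 8.3, 10.6 and 13.9% at ρ = 0.3, 0.5 and 0.8, against 5.1% with one lesion. The pattern does not depend on having only 10 patients.

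**Step 4. Small groups without clustering.** With one lesion each and 60% progression, the chi-square log-rank already gives 8.5% at 3/3, 9.1% at 8/2 and 10.3% at 4/2. This is a separate small-sample error.

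**Step 5. Fisher test.** At lesion level, with two lesions, 5/5 and shared status, the error is 1.7-5.5%. Fisher is conservative and no inflation is shown. This is specific to two lesions: the copula model with three lesions and 10 patients gives 4.1, 6.8 and 11.1% at ρ = 0.3, 0.5 and 0.8.

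**Step 6. Attainable p-values.** With shared status and equal lesion counts, the smallest permutation p is at best 1/C(n,k), or 2/C(n,k) for equal groups: 4/2, 1/15 = 0.067; 3/3, 2/20 = 0.10; 5/5, 2/252 = 0.008. These are floors, because patients censored together at 6 months are tied. For 5/5 with one lesion each:

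- Three progressors, all on one side: 2 × C(7,2) = 42 relabelings, 42/252 = 0.167.
- Four progressors: 2 × C(6,1) = 12, 12/252 = 0.048.

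For 4/4 with three progressors: 2 × C(5,1) = 10, 10/70 = 0.143. At 30% progression, three or fewer of ten independent patients progress with probability 65% (binomial), so 0.05 would often be out of reach.

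**The case against.** The strongest reply is that no error is shown. No section says that any patient has more than one lesion. Section 6a describes patients "referred to the cancer center for assessment of an osteonecrosis lesion in the bone", in the singular, and section 2a also speaks of one osteonecrosis. The plural in section 10 is natural when lesions are compared across patients, and the random effect covers measures, which may be repeated scans or track areas. All of this stands: the error is conditional, and what is certain is the missing provision and the missing lesion count.

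It is also fair that the study is declared exploratory and that no decision rule rests on this test. That lowers the weight. It does not settle the matter, because the stated reason concerns multiplicity, and P below 0.05 is still called significant.

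Some stronger readings are tempting, and the documents do not support them:

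- A reader might infer that 0.05 holds only with one lesion per patient. One lesion is sufficient, not necessary: uncorrelated lesions, or enhancement unrelated to the patient, also leave the error near nominal.
- A reader might infer that at most 10 patients enter, since only ferumoxytol recipients can enhance. Section 10 does not say whether operated controls count as non-enhancing.
- A reader might infer that the Fisher test fails too. Its unit is unstated, which is a gap and not a demonstrated error.
- Section 10 is in the past tense, so a reader might infer that a reported result is wrong. The documents contain no p-value.

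**Conclusion.** The concern holds as a conditional one. Section 10 makes the lesion the unit of an ordinary log-rank test without any allowance for shared patients. If patients contribute several lesions with correlated progression, 0.05 is not assured. With two lesions, 10 patients at 5/5 and τ from 0.2 to 0.5, the error is about 6-14% for shared enhancement (baseline about 6%), about 0.4-3.5% for one lesion of each kind per patient, and near nominal for unrelated enhancement. Lesions per patient, correlation, event rates and split are all assumptions. At weak correlation and 30% progression, clustering adds almost nothing. The point deserves correction because the repair is cheap, but its weight is modest.

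**What to change.** In section 10:

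1. State the unit of the log-rank and Fisher tests, the lesions per patient followed from surgery, and whether operated patients without ferumoxytol count as non-enhancing.
2. Replace the lesion-level chi-square log-rank p-value with an exact or permutation p-value that respects the patient. Move enhancement labels as whole sets between patients with the same lesion count, and among lesions within a patient. With one lesion each this is an ordinary permutation, which also removes the small-sample excess. Alternatively, use one index lesion per patient, chosen by a baseline rule blind to outcome (for example the largest on the pre-surgery MRI), with an exact p-value.
3. Compute the smallest attainable p from the actual split and the observed number and pattern of events, not from 1/C(n,k) alone. If 0.05 is out of reach, list times and status by patient and claim no significance.
4. If the Fisher test is at lesion level, use the same permutation.
5. If the analysis has already been run, report the patient-respecting p-value beside the one obtained, labelled as a re-analysis.

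In simulation with two lesions and shared status (5/5, 7/3, 8/2, 4/4, 6/2, 5/2, 4/3), the permutation test had null error 2.5-5.2% at 60% progression and 1.2-4.6% at 30%.

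The cost is a few sentences, a few lines of R and low power. At an assumed within-patient hazard ratio of 0.25 (60% progression in non-enhancing lesions, two lesions, shared, 5/5), power is 27% at τ = 0.2 and 13% at τ = 0.5. The unadjusted test shows 41% and 30% but does not hold its level. The permutation also assumes that length of follow-up does not depend on enhancement.
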